**Table 9-4 Antidiabetic Medications**

Rank	Medication	Route	Weight Change	Notes
------	------------	-------	---------------	-------

1	Metformin	PO	Neutral	
2	Sulfonylureas (2nd generation)	PO	Gain	
3	DPP-4 Inhibitors	PO	Neutral	
4	SGLT1/2	PO	Loss	Discuss with medical monitor prior to introduction.  Potential benefit in CVD
5	GLP-1 Agonists	SQ	Loss	Discuss with medical monitor prior to introduction.  Potential benefit in CVD
6	Thiazolidinediones	PO	Gain	Pioglitazone disallowed per protocol

### 9.6. Additional Restrictions and Precautions

Subjects should refrain from alcohol consumption and strenuous physical activity (eg, weight lifting, strenuous yard work, intensive exercise workouts) for 48 hours prior to study visits and laboratory evaluations.

### 9.7. Treatment Adherence

Subjects will bring all of their study-supplied bottles of study drug to every clinic visit, and clinic staff will assess adherence based on the number of remaining tablets less any overage provided to cover the visit window. Subjects who miss doses must be counseled on the importance of adhering to their daily dosing schedule.

## 10. STUDY PROCEDURES

Study procedures are summarized across all study visits within the Schedule of Assessments for Part 1 (Table 20–1) and Part 2 (Table 20–2).

[figure not shown]
### 10.1. Part 1 and Part 2: Screening (Month -3; Visit 1)

[figure not shown]
Prior to any clinical procedures and evaluations, written signed informed consent must be obtained. In Part 1 and Part 2, a Screening visit is to occur within 3 months before the Baseline visit (see Section 10.2).

[figure not shown]
Subjects who do not meet **all eligibility criteria** at Screening will be allowed to rescreen twice. However, if a subject fails to meet eligibility criteria upon rescreening, he or she will remain ineligible for the study.

[figure not shown]
Subjects who do not meet any of the laboratory eligibility criteria during the Screening period will be allowed to retest twice, with at least 1-week interval between the date of the first failed test and the date of subsequent test. However, if a subject fails to meet eligibility

[figure not shown]
criteria upon these 2 retest opportunities, he or she will remain ineligible for the study. In Part 2, the Screening visit will only be required for newly enrolled subjects. The Screening visit will not be required for subjects continuing their previously assigned blinded treatment from Part 1.

[figure not shown]

[figure not shown]

[figure not shown]

[figure not shown]

[figure not shown]

[figure not shown]

[figure not shown]

[figure not shown]

[figure not shown]

[figure not shown]

[figure not shown]

[figure not shown]

[figure not shown]

[figure not shown]

[figure not shown]

[figure not shown]

[figure not shown]

[figure not shown]

[figure not shown]

[figure not shown]

[figure not shown]

## **11. STUDY ASSESSMENTS**

### **11.1. Demographic and Other Pretreatment Assessments: Part 1 and/or Part 2**

After written informed consent is obtained, demographic data and a complete medical and medication history will be collected at the Screening visit. A complete physical examination, including measurements of height and body weight will be performed. Medical history will be updated until the first dose of study drug. All AEs will be recorded from the time of informed consent and throughout the study, regardless of apparent causality from use of the study drug. Medications taken before the first dose of study drug will be recorded as prior medications.

### **11.2. Assessments of Efficacy**

In Part 1, subjects meeting all eligibility criteria and with suspicion of significant liver fibrosis (through clinical, hepatic fibrosis indices, and/or liver stiffness assessment) will have a liver biopsy read by an independent central pathologist during the Screening period. In randomized subjects, a second post-treatment liver biopsy will be collected within  $\pm 2$  weeks of the Month 12 visit.

In Part 2, newly enrolled subjects will undergo a liver biopsy at Screening for assessment of eligibility and a second post-treatment liver biopsy will be collected within  $\pm 2$  weeks of the

Month 12 visit. All subjects (newly randomized subjects with a liver biopsy diagnosis of NASH and Stage 3 liver fibrosis (by NASH CRN system) and those who continue from Part 1) will undergo a liver biopsy at Month 60 (within  $\pm$  2 weeks) after first dose of study drug.

At the end of study, if a subject has received study drug for at least 6 months and has not had the Month 60 biopsy, then a biopsy should be taken within 30 days of the end of study, if feasible.

Liver biopsies will be performed per standard of care (eg, taking into account the subject's health status, coagulation profile, and use of concomitant medications). Subjects who discontinue study drug are encouraged to continue with all other evaluations as scheduled in this protocol, including biopsies and other invasive procedures at the scheduled visits. If a subject discontinues study participation early and has received study drug for at least 6 months in Part 1 or Part 2, then a biopsy should be taken within 30 days of discontinuation, if feasible. All liver biopsies will be evaluated by an independent central pathologist; whenever possible, the same pathologist will evaluate all biopsies from an individual subject. The independent central pathologists will be blinded to individual treatment assignment.

Liver biopsy at Screening and Months 12 and 60 will be used to determine improvement in histologic fibrosis stage (NASH CRN – the system used to assess the primary efficacy endpoint – and Ishak systems).

### **NASH CRN Staging System**

The NASH CRN adopted the staging system validated by Kleiner. The authors evaluated a scoring system comprising 14 histological features that addressed the full spectrum of lesions of NAFLD. Five features were evaluated semi-quantitatively (steatosis [0-3], location [0-3], lobular inflammation [0-3], hepatocellular ballooning [0-2], and fibrosis stage [0-4]) and 9 additional features were recorded as present or absent. As a result of this evaluation, the NASH CRN staging system for evaluating histological changes after therapeutic intervention trials adopted a defined and validated semi-quantitative scoring system, NAS, based on the unweighted sum of steatosis, lobular inflammation, and hepatocellular ballooning scores. The system is simple and requires only routine histochemical stains (hematoxylin and eosin and Masson trichrome stains). This strong scoring system and NAS for NAFLD and NASH was shown to have reasonable inter-rater reproducibility in both adults and children with any degree of NAFLD. A NAS of  $> 5$  correlated with a diagnosis of NASH, and biopsies with scores of  $< 3$  were diagnosed as not NASH. The primary purpose of the NAS is to assess overall histological change; it is not intended that numeric values replace the pathologist's diagnostic determination of steatohepatitis.

The evaluation of fibrosis stage associated with NASH will be based on the NASH CRN Fibrosis Staging System, as follows:

Fibrosis	Stage
None	0
Perisinusoidal or periportal	1
Mild, zone 3, perisinusoidal	1A
Moderate, zone 3, perisinusoidal	1B
Portal/periportal	1C
Perisinusoidal and portal/periportal	2
Bridging fibrosis	3
Cirrhosis	4

### **Ishak Staging System**

The morphological features that are important in undertaking grading and staging in chronic hepatitis are described by Ishak. The Ishak fibrosis stage will be based on the following scoring system:

Architectural Changes, Fibrosis and Cirrhosis	Score
No fibrosis	0
Fibrous expansion of some portal areas, with or without short fibrous septa	1
Fibrous expansion of most portal areas, with or without short fibrous septa	2
Fibrous expansion of most portal areas with occasional portal to portal (P-P) bridging	3
Fibrous expansion of portal areas with marked bridging [portal to portal (P-P) as well as portal to central (P-C)]	4
Marked bridging (P-P and/or P-C) with occasional nodules (incomplete cirrhosis)	5
Cirrhosis, probable or definite	6

### **Serum hepatic fibrosis indices**

Serum hepatic fibrosis indices (including FIB-4, APRI, and NFS) will be determined at Screening, Baseline, and Months 6 and 12 in Part 1, and at Screening, Baseline, Months 6 and 12, and every 12 months thereafter in Part 2.

APRI is calculated using the formula:

$$\text{APRI} = (\text{AST level [ULN]} / \text{platelet counts [10}^9\text{/L]}) \times 100$$

An APRI index of  $\leq 0.50$  indicates the absence of significant fibrosis and an index of  $> 1.50$  indicates the presence of significant fibrosis.

NFS is a validated simple scoring system consisting of routinely measured and readily available clinical and laboratory data to categorize NAFLD patients with and without advanced fibrosis:

$NFS = -1.675 + 0.037 \times \text{age (years)} + 0.094 \times \text{BMI (kg/m}^2\text{)} + 1.13 \times \text{IFG/diabetes (yes = 1, no = 0)} + 0.99 \times \text{AST/ALT ratio} - 0.013 \times \text{platelet (}\times 10^9\text{/L)} - 0.66 \times \text{albumin (g/dL)}$ . FIB-4 is a noninvasive hepatic fibrosis index score combining standard biochemical values, platelets, ALT, AST, and age that is calculated using the formula:

$$\text{FIB-4} = (\text{Age [years]} \times \text{AST [U/L]}) / (\text{platelets [10}^9\text{/L]} \times (\text{ALT [U/L]})^{1/2})$$

A FIB-4 index of  $< 1.45$  indicates no or moderate fibrosis and an index of  $> 3.25$  indicates extensive fibrosis/cirrhosis.

The Enhanced Liver Fibrosis (ELF™) Test is a blood test that provides an ELF Score that delivers information on liver fibrosis severity and will be assessed in this study. The ELF Score is determined by combining in an algorithm, quantitative measurements of by-products of the fibrotic process (hyaluronic acid [HA]), amino-terminal propeptide of type III procollagen [PIIINP]), tissue inhibitor of metalloproteinase 1 [TIMP-1]).

The ELF Score will be determined at Baseline, Month 6, Month 12, and every 12 months thereafter.

The authors analyzed routine demographic, clinical, and laboratory variables to predict presence or absence of advanced fibrosis. Age, hyperglycemia, BMI, platelet count, serum albumin, and AST/ALT ratio were found to be independent indicators of advanced liver fibrosis, so these 6 variables were included in the NFS scoring system. A low cut-off score of -1.455 indicates the absence of advanced fibrosis and a high cut-off score of 0.676 indicates the presence of advanced fibrosis.

At sites where available, liver stiffness will be assessed in fasting subjects by ultrasound TE at Baseline (if not performed within 6 months prior to the first day of Screening), at Months 6 and 12 in Part 1, and annually in Part 2. The Screening value (if performed by TE) will be used as the Baseline value. The visit window will be  $\pm 2$  weeks for all on-treatment TE assessments.

### **11.3. Assessments of Safety**

AEs will be assessed at each visit.

#### **11.3.1. Adverse Events and Serious Adverse Events**

##### *11.3.1.1. Definitions*

###### 11.3.1.1.1. Adverse Event

An AE is any untoward medical occurrence in a subject or clinical investigation subject administered a pharmaceutical product and which does not necessarily have a causal relationship with this treatment. An AE can therefore be any unfavorable and unintended sign (including an abnormal laboratory finding), symptom, or disease temporally associated with the use of a medicinal (investigational) product, whether or not related to the medicinal (investigational) product.

###### 11.3.1.1.2. Treatment-Emergent Adverse Events

An event will be considered a TEAE if:

- The event began on or after the date of the first dose of study drug; or
- An exacerbation of a chronic or intermittent pre-existing condition, including either an increase in frequency and/or intensity of the condition on or after the date of the first dose of study drug

An AE that occurs more than 30 days after the last dose of study drug will not be counted as a TEAE.

###### 11.3.1.1.3. Adverse Drug Reaction

An adverse drug reaction (ADR) is defined as any adverse event caused by the use of a pharmaceutical product. Adverse reactions are a subset of all suspected adverse reactions for which there is reason to conclude that the pharmaceutical product caused the event.

###### 11.3.1.1.4. Suspected Adverse Reaction

Suspected adverse reaction (SAR) means any adverse event for which there is a reasonable possibility that the study drug caused the adverse event. “Reasonable possibility” means there is evidence to suggest a causal relationship between the study drug and adverse event. A suspected adverse reaction implies a lesser degree of certainty about causality than adverse reaction, which means an adverse event caused by a study drug.

###### 11.3.1.1.5. Unexpected Adverse Event or Reaction

An adverse event or suspected adverse drug reaction is considered “unexpected” if it is not listed in the investigator brochure or is not listed at the specificity or severity that has been observed; or, if an investigator brochure is not required or available, is not consistent with the risk information described in the general investigational plan.

#### 11.3.1.1.6. Events Related to Disease Under Study

Worsening of a pre-existing illness other than the disease under study will be assessed as an AE. If such an AE meets the definition of an SAE (see Section 11.3.1.1.10), it must be reported as such (see Section 11.3.1.5).

#### 11.3.1.1.7. Clinically Significant Laboratory Abnormalities

Any laboratory abnormalities deemed clinically significant by the investigator must be reported as an AE. A clinically significant abnormality is a confirmed abnormality (by repeat testing) that is changed sufficiently from Baseline so that in the judgment of the investigator a change in management is warranted. This alteration may include: monitoring the laboratory test further, initiating other diagnostic tests or procedures, changing ongoing treatment, or administering new treatment. See Section 11.3.6 for details regarding the management and monitoring of laboratory abnormalities of interest. See Section 11.3.1.2 for details regarding recording of adverse events.

#### 11.3.1.1.8. Surgical Procedures

Surgical procedures themselves are not AEs; they are therapeutic measures for conditions that require surgery. The condition for which the surgery is required may be an AE, if it occurs or is detected during the study period. Planned surgical measures permitted by the clinical study protocol and the condition(s) leading to these measures are not AEs, if the condition(s) was (were) known before the start of the study drug. In the latter case, the condition should be reported as medical history.

#### 11.3.1.1.9. Overdose

An overdose is defined as a subject's report of taking more than 1 tablet of study drug (ie, more than 1 tablet per day of blinded CVC or placebo). Overdose per se will not be reported as an AE or SAE unless it is an intentional overdose taken with possible suicidal/self-harming intent. Such overdoses should be reported regardless of sequelae. For reporting purposes, overdose will be considered an SAE only if any of the seriousness criteria are met (see definition in Section 11.3.1.1.10).

#### 11.3.1.1.10. Serious Adverse Event or Serious Adverse Reaction

An AE or suspected adverse reaction is considered serious if, in the view of either the investigator or sponsor, it results in any of the following outcomes:

- Death
- Life-threatening AE
  - An AE or suspected AE is considered life-threatening if, in the view of either the investigator or sponsor, its occurrence places the patient or subject at

immediate risk of death. It does not include an AE or suspected adverse reaction that, had it occurred in a more severe form, might have caused death.

- Inpatient hospitalization (ie, admission, overnight stay) or prolongation of existing hospitalization
- Persistent or significant incapacity or substantial disruption of the ability to conduct normal life functions
- Congenital anomaly/birth defect
- Important medical events
  - An important medical event is one that, when based upon appropriate medical judgment, may jeopardize the subject and may require medical or surgical intervention to prevent one of the outcomes listed above in the definition of an SAE. (Examples of such events include allergic bronchospasm requiring intensive treatment at an emergency room or at home, blood dyscrasias, convulsions that do not result in inpatient hospitalization, or the development of drug dependency or drug abuse.)

#### 11.3.1.1.11. Adverse Events of Special Interest

An adverse event of special interest (AESI) (serious or non-serious) is one of scientific and medical concern specific to the sponsor's study drug/device or program, which warrants ongoing monitoring and rapid communication by the investigator to the sponsor. Such an event might warrant further investigation in order to characterize and to understand it.

Elevations in biochemistry that are associated with liver injury have been identified as potentially important risks and are considered AESI for the study drug in this protocol. If subjects meet biochemical criteria for suspected DILI, as defined in Section 11.3.6.4, the event should be reported to Global Patient Safety and Epidemiology (GPSE) within 24 hours on the AESI form (see Section 1). In addition, the AESI form should be completed and sent to GPSE within 24 hours of permanent study drug discontinuation for confirmed ALP, ALT, AST, and/or bilirubin elevations. AESI will be adjudicated by a hepatologist with expertise in DILI and reviewed by the DSMB.

#### 11.3.1.2. *Adverse Event and Clinically Significant Laboratory Abnormality Recording*

Treatment-emergent adverse events and laboratory test abnormalities considered to be clinically significant should be recorded as AEs in the eCRF.

The AE or clinically significant laboratory abnormality should be reported in standard medical terminology. If known, the diagnosis of the underlying illness or disorder should be recorded, rather than its individual symptoms. If a definitive diagnosis is not possible, the individual symptoms and signs should be recorded.

If the laboratory abnormalities are part of a clinical constellation of signs and/or symptoms that comprise a medical diagnosis, then the terminology for that medical diagnosis should be used in the AE record.

AEs and clinically significant laboratory abnormalities that are reported as AEs fall into the categories of “non-serious” and “serious.” From the time of informed consent and throughout the study, all AEs and clinically significant laboratory abnormalities must be recorded in the eCRF, regardless of apparent causality from use of the study drug.

The following information should be captured for all AEs and clinically significant laboratory abnormalities: date of onset and end date or outcome (eg, ongoing), severity of the event, seriousness of the event, investigator’s opinion of the relationship to investigational product (CVC), action taken with regard to any of the study drugs and treatment required for the AE, cause of the event (if known), and information regarding the resolution/outcome.

AEs classified as serious must be recorded on the appropriate SAE reporting tool and reported to the sponsor using expeditious handling to comply with regulatory requirements (see Section 11.3.1.5).

#### 11.3.1.3. *Adverse Event Classification*

The intensity of an AE or clinically significant laboratory abnormality will be graded according to the scale below in addition to the National Cancer Institute Common Terminology Criteria for Adverse Events (NCI CTCAE) version 4.03 Table for Grading the Severity of Adult Adverse Events (see Appendix 20.2). The clinical significance of the AE is determined by the investigator. The investigator is encouraged to consult with the medical monitor. Grade refers to the severity of the AE. The CTCAE displays Grades 1 through 5 with unique clinical descriptions of severity for each AE based on this general guideline.

- **Grade 1 (Mild):** Asymptomatic or mild symptoms; clinical or diagnostic observations only; intervention not indicated
- **Grade 2 (Moderate):** Minimal, local or noninvasive intervention indicated; limiting age-appropriate instrumental activities of daily living (ADL)
- **Grade 3 (Severe):** Medically significant but not immediately life-threatening; hospitalization or prolongation of hospitalization indicated; disabling; limiting self-care ADL
- **Grade 4 (Life-Threatening):** Life-threatening consequences; urgent intervention indicated
- **Grade 5 (Death):** Death related to AE

When the intensity of an AE or clinically significant laboratory abnormality changes over time for a reporting period (eg, between visits), each change in intensity will be reported as an AE until the event resolves. For example, 2 separate AEs will be reported if a subject

experiences Grade 1 diarrhea for 3 days, meeting the definition of an AE, and then after 3 days the event increases to a Grade 3 intensity that lasts for 2 days and then resolves. The Grade 1 event will be reported as an AE with a start date equal to the day the event met the AE definition and a stop date equal to the day that the event increased in intensity from Grade 1 to Grade 3. The Grade 3 event will also be reported as an AE with the start date equal to the day the event changed in intensity from Grade 1 to Grade 3 and a stop date on the day that the event changed intensity again or resolved. For analysis purposes, this will be considered one AE for this subject and the maximum intensity will be recorded.

The relationship or association of the AE to a study drug (CVC or placebo) should be assessed using clinical judgment and the following considerations:

- **No:** Evidence exists that the adverse event has an etiology other than the investigational medicinal product. For SAEs, an alternative causality must be provided (eg, pre-existing condition, underlying disease, intercurrent illness, or concomitant medication)
- **Yes:** A temporal relationship exists between the AE onset and administration of the investigational medicinal product that cannot be readily explained by the subject's clinical state or concomitant therapies. Furthermore, the AE appears with some degree of certainty to be related, based on the known therapeutic and pharmacologic actions or AE profile of the study drug. In case of cessation or reduction of the dose, the AE abates or resolves and reappears upon re-challenge.

It should be emphasized that ineffective treatment should not be considered as causally related in the context of adverse event reporting.

The relationship to study procedures (eg, invasive procedures such as venipuncture or liver biopsy) should be assessed using the following considerations:

- **No:** Evidence exists that the adverse event has an etiology other than the study procedure
- **Yes:** The adverse event occurred as a result of protocol-mandated procedures such as venipuncture or liver biopsy

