#### *11.3.1.5. Reporting of Serious Adverse Events*

The sponsor is required to expedite to regulatory authorities reports of SAEs, serious ADRs, or suspected unexpected serious adverse reactions (SUSARs) in line with relevant legislation or regulations, including the applicable US FDA Code of Federal Regulations, the European Commission Clinical Trials Directive (2001/20/EC), and other country specific legislation or

regulations. Expectedness of SAEs will be determined by the sponsor using reference safety information specified in the Investigator Brochure.

Any SAE, serious ADR or SUSAR that occurs during the study from the time of signing the ICF to within 30 days following discontinuation of study drug, regardless of relationship to the study drug, must be reported within 24 hours to the contact below:

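### The Yes and No definitions of drug-relatedness leave a gap and are stricter than the protocol's own reasonable-possibility standard, so related TEAEs and TESAEs can be under-counted

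*Protocol*

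**What the plan says.** Protocol Section 11.3.1.3 says that the relationship of an AE to study drug "should be assessed using clinical judgment and the following considerations". Two categories follow.

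- *No*: "Evidence exists that the adverse event has an etiology other than the investigational medicinal product". For SAEs the investigator must also name the alternative cause.
- *Yes*: "A temporal relationship exists between the AE onset and administration of the investigational medicinal product that cannot be readily explained by" the subject's condition or other therapies. A second sentence, introduced as a further point, asks for some certainty of relatedness "based on the known therapeutic and pharmacologic actions or AE profile of the study drug". A third adds "In case of cessation or reduction of the dose, the AE abates or resolves and reappears upon re-challenge".

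Elsewhere the protocol uses other standards. Section 11.3.1.1.4 defines a suspected adverse reaction as "any adverse event for which there is a reasonable possibility that the study drug caused the adverse event" and says that this implies less certainty than an adverse reaction. Section 11.3.1.5, on SAEs detected after the observation period, speaks of events possibly related to prior study drug. Section 11.3.2.2 speaks of laboratory abnormalities possibly or probably related to treatment.

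Protocol Section 12.4.2.1 counts TEAEs that the investigator judged related. SAP Table 5-18 tabulates treatment-related TEAEs and treatment-related TESAEs. SAP Table 6-6 imputes a missing relationship as related if the event falls in the Treatment Period.

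**The concern.** A two-way causality field works only if every event fits one category and both categories follow the standard used in the rest of the protocol. Here *No* is not the complement of *Yes*. Each needs its own positive evidence, and events with neither kind of evidence are left between them. These include events that a safety review would want to see: reactions outside the known profile, and reactions for which drug was stopped for good.

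At stake is the content of the treatment-related TEAE and TESAE tables. Onward SUSAR classification may also be affected, if the sponsor takes the investigator's answer as the causality judgment. Investigators at up to 600 centers (Protocol Section 8) may also resolve the gap in different ways.

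**Working it through.** No alpha, power, rate or event count enters this point, so the check sets the definitions side by side.

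**Step 1: the limbs of *Yes*.**

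- (a) A temporal relation without a ready alternative explanation.
- (b) Some certainty based on known therapeutic or pharmacologic actions, or on the AE profile. The text adds this to (a) and does not offer it as an alternative.
- (c) If dosing is stopped or reduced, the event abates or resolves and reappears on re-challenge. The condition limits (c) to events with cessation or reduction. Once it applies, abatement and reappearance are joined by 'and'.

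**Step 2: apply the definitions to typical events.** All but the first row assume a plausible temporal relation and no evidence of another cause.

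| Event | *No*? | *Yes*, read literally? | Could be a reasonable possibility (11.3.1.1.4)? |
|---|---|---|---|
| Another cause is shown | Met | Fails (a) | Normally not |
| Fits the profile, dosing continues | Not met | Met; (c) not engaged | Yes |
| Fits the profile, drug stopped and restarted, event returns | Not met | Met | Yes |
| Fits the profile, drug stopped, event resolves, drug not restarted | Not met | Fails (c) | Yes |
| Outside known actions and profile, dosing continues | Not met | Fails (b) | Yes |

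The last two rows meet neither definition, yet either can be a reasonable possibility. This shows both the gap and the conflict with Section 11.3.1.1.4.

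**Step 3: how far limb (b) reaches.** Section 11.3.1.1.5 calls an event unexpected if it is "not listed in the investigator brochure or is not listed at the specificity or severity that has been observed". Unexpected is therefore not the same as failing (b). An event missing from the brochure may fit the known pharmacology, and a more severe form of a listed reaction is unexpected but fits the profile. Limb (b) fails only for events outside both the known actions and the profile.

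**Step 4: follow the answer into the tables.**

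- Entered *Yes*: counted as related.
- Left blank in the Treatment Period: imputed as related for the tables (SAP Table 6-6).
- Entered *No*: stays *No*. Nothing in the SAP corrects it.

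The same event can therefore appear as related or unrelated, depending on whether the investigator leaves the field blank or picks the nearer category.

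**Step 5: check which reporting routes use the answer.**

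- All AEs are recorded whatever the apparent causality (Protocol Section 11.3.1.2).
- From consent to 30 days after stopping drug, every SAE goes to the sponsor within 24 hours whatever the relationship, and the sponsor determines expectedness (Section 11.3.1.5). The visible text does not say whether the sponsor also makes its own causality assessment.
- For SAEs detected after the observation period, contact with the medical monitor depends on the investigator's view of causality (Section 11.3.1.5).
- Suspected DILI is reported within 24 hours on biochemical criteria, adjudicated by a hepatologist and reviewed by the DSMB (Section 11.3.1.1.11). It has its own summary, with adjudication as unlikely, possible or probable (SAP Table 5-20).

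**The case against.** The strongest reply is that Section 11.3.1.3 is guidance, not a checklist. Its lead-in calls the items considerations under clinical judgment, and the re-challenge sentence applies only when dosing is stopped or reduced. A sensible investigator can answer *Yes* without re-challenge. For SAEs, *No* needs a named alternative cause, so a serious event without one cannot properly be scored *No*; if it is left blank on treatment, the SAP counts it as related. The main safety tables (TEAEs, TESAEs, TEAEs leading to study drug discontinuation, deaths) do not use relatedness, and no safety hypotheses are prespecified (Protocol Section 12.4.2, SAP Section 5.1.1.4).

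Most of this stands and limits the point. It does not close the gap. Judgment still has to be exercised against some standard, and the protocol gives more than one. The requirement to name another cause covers SAEs only, so it does not help with non-serious events. The imputation acts on blanks only.

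Three stronger readings are tempting, and the documents do not support them:

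- *Events fall out of expedited reporting.* SAEs in the study period reach the sponsor regardless of the answer. Only later SUSAR classification is open to question.
- *The DSMB sees only events scored as related.* Nothing in the visible text says so.
- *Drug-induced liver injury is lost.* Suspected DILI has its own route and table, and liver biochemistry elevations are already a named potential risk, so limb (b) need not fail. A liver event for which drug was permanently stopped could still miss the related-TEAE table under limb (c). The rules in Section 11.3.6.4 are not visible, so restart practice cannot be checked.

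**Conclusion.** The point holds as a defect of definition with a limited consequence. Read literally, *Yes* and *No* do not cover all events, and *Yes* asks for more than the reasonable possibility of Section 11.3.1.1.4. Relative to that standard, the expected direction is under-counting in the treatment-related TEAE and TESAE tables, with a possible effect on SUSAR classification.

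The size cannot be estimated. The documents do not say how many events will lie outside the known profile, how often drug will be stopped and not restarted, or how investigators will resolve the gap. A reader might reach for the Phase 2b suspected-DILI rate in Protocol Section 5.3.3: 3.3% in each arm (4/121, 2/61 and 2/60). That rate includes placebo subjects, counts biochemical criteria, and identifies no event with a misclassified relationship, so it does not measure this problem.

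The conclusion assumes that at least some investigators follow the wording of *Yes* closely and enter *No* when it is not met. The efficacy analyses and the safety tables that do not use relatedness are unaffected. The wording should be corrected, but this is not among the most serious problems a plan can have.

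**What to change.** In Section 11.3.1.3, define *Yes* as a reasonable possibility, in the sense of Section 11.3.1.1.4, that study drug caused the event, and *No* as the absence of one. The two are then complements and every event fits one.

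Keep known actions and AE profile, course after stopping or reduction, and re-challenge as a list of supporting evidence, and state that none of it is required. Use the same standard in Section 11.3.1.5 (SAEs detected after the observation period) and Section 11.3.2.2 (laboratory abnormalities). SAP Table 6-6 can stay as it is.

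The cost is a wording amendment and a letter to investigators. Somewhat more events will be scored as related. No dose, schedule or stopping rule changes.
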